Excluded based on Exclusion 14- History of Malignant Neoplasm (prior 5 years)	-4,554	121,487	-3,985	132,537	-19,311	315,535
Excluded based on Exclusion 15- HIV/AIDS (dx and meds) -prior 5 years	-64	121,423	-56	132,481	-127	315,408
Excluded based on Exclusion 16- Hematological disorder	-1,540	119,883	-1,633	130,848	-7,624	307,784
Excluded based on Exclusion 17- CCI (180 days) >=10	-177	119,706	-50	130,798	-696	307,088

Excluded based on Exclusion 18 - Major Surgery (90 days prior)	-191	119,515	-212	130,586	-674	306,414
Excluded based on Exclusion 20- Use of SGLT2i (prior 6 months)	-833	118,682	-892	129,694	-817	305,597
Excluded based on Exclusion 22- use of a corticosteroid medication or immunosuppressive agent	-3,235	115,447	-3,085	126,609	-8,985	296,612
Excluded based on Exclusion 23- Use of cana in prior 3 months (although this is already applied as part of cohort creation)	0	115,447	0	126,609	0	296,612
Excluded based on Exclusion 24- Alcohol or Drug abuse (prior 3 years) and Exclusion 25- Pregnancy	-972	114,475	-532	126,077	-1,766	294,846
Final cohort		114,475		126,077		294,846

* Medicare database includes only patients with at least one diagnosis for diabetes, heart failure, or cerebrovascular disease.

**Exclusion 24 and 25 collapsed to adhere to CMS cell suppression guidelines.

For canagliflozin vs. 2nd generation SUs

	Optum		MarketScan		Medicare*	
	Less Excluded Patients	Remaining Patients	Less Excluded Patients	Remaining Patients	Less Excluded Patients	Remaining Patients
All patients		74,864,884		191,990,035		23,466,175
Patients who used exposure or a reference between April 1, 2013 to Dec 2017 (for MarketScan/Medicare)/March 2019 (for Optum)	-73,662,096	1,202,788	-190,768,942	1,221,093	-20,351,733	3,114,442
Patients who have continuous 6 months registration in the database	-165,247	1,037,541	-115,162	1,105,931	-861,454	2,252,988
Patients without prior use of reference	-710,706	326,835	-759,153	346,778	-1,627,827	625,161
Patients without prior use of exposure	-70,933	255,902	-88,833	257,945	-68,783	556,378
Excluded because patient qualified in >1 exposure category	-168	255,734	-149	257,796	-118	556,260
Excluded based on Age	-10	255,724	0	257,796	0	556,260
Excluded based on Gender	-17	255,707	0	257,796	0	556,260
Excluded based on Inclusion 1- DM Type 2 with ICD-10	-14,479	241,228	-23,583	234,213	-8,608	547,652

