Final cohort		172,234		156,544		415,696

* Medicare database includes only patients with at least one diagnosis for diabetes, heart failure, or cerebrovascular disease.

** Exclusion 24 and 25 collapsed to adhere to CMS cell suppression guidelines.

6. Variables

6.1 Exposure-related variables:

Study drug:

The study exposure of interest is initiation of canagliflozin. Initiation will be defined by no use of any SGLT-2 inhibitor or a comparator in the prior 6 months before treatment initiation (washout period).

Comparator agents:

- Initiators of canagliflozin will be compared to initiators of-
 - DPP4i (**primary**)
 - 2nd generation sulfonylureas

Because canagliflozin and comparators are frequently used as second or third line treatments of T2DM, we expect it to be unlikely that canagliflozin and comparators are initiated in patients with substantially different baseline risk for proposed outcomes.

6.2 Preliminary Covariates:

- Age
- Sex
- Combined Comorbidity Index (CCI), measured over the default baseline covariate assessment period, defined as 180 days prior to and including index date

Covariates listed above represent only a small subset of covariates that will ultimately be controlled for in the design and analysis. We use the covariates above only for initial feasibility analyses to judge whether there is likely to be sufficient overlap between treatment groups to proceed with the study. Remaining covariates are defined only after the study has passed the initial feasibility analysis and the initial power assessment and are listed in Table 1 (**Appendix B**). These covariates are based on those used by Patorno et al. (2019).

6.3 Outcome variables and study follow-up:

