6.3.2 Study follow-up

Both as-treated (AT) and intention-to-treat (ITT) analyses will be conducted with treatment defined as the index drug on the day of cohort entry. Because adherence in the real world databases is expected to be much worse than in the trial, the AT analysis is the **primary** analysis, as it targets the relative hazard of outcomes on treatment.

For the AT analyses, the follow-up will start the day after initiation of canagliflozin and comparator and will continue until the earliest date of the following events:

- The first occurrence of the outcome of interest, unless otherwise specified for selected outcomes,

- The date of end of continuous registration in the database,
- End of the study period,
- Measured death event occurs,
- Nursing home admission
 - Nursing home admissions are considered a censoring event because the data sources utilized typically provide little to no data on a patient, particularly on drug utilization, after admission. We will utilize this as an exclusion reason for cohorts for the same reason.
- The date of drug discontinuation, defined as the date of the last continuous treatment episode of the index drug (canagliflozin and comparator) plus a defined grace period (i.e., 30 days after the end of the last prescription's days' supply in main analyses).
- The date of augmentation or switching from an exposure to a comparator or any other agent in the comparator class and vice versa (e.g. switching from saxagliptin to linagliptin would be a censoring event);
 - A dosage change on the index treatment does not fulfill this criterion
 - An added treatment that is not part of the exposure or comparator group does not fulfill this criterion (e.g. if a canagliflozin user adds insulin, he or she does not get censored at the time of insulin augmentation)

For the ITT analyses, the censoring based on the augmentation/switching and treatment discontinuation will be replaced with a maximum allowed follow-up time of 365 days.

7. Initial Feasibility Analysis

Action report name:

For canagliflozin vs. DPP4i

Optum- <https://bwh-dope.aetion.com/#/projects/details/660/results/26056/result/0>

Marketscan- <https://bwh-dope.aetion.com/#/projects/details/661/results/26057/result/0>

Medicare- <https://bwh-dope.aetion.com/#/projects/details/662/results/26055/result/0>

For canagliflozin vs. 2nd generation SUs

Optum- <https://bwh-dope.aetion.com/#/projects/details/660/results/26064/result/0>

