Action report name:

For canagliflozin vs. DPP4i

- Optum- <https://bwh-dope.aetion.com/projects/details/660/results/44837/result/0>
- Marketscan- <https://bwh-dope.aetion.com/projects/details/661/results/44838/result/0>
- Medicare- <https://bwh-dope.aetion.com/projects/details/662/results/44839/result/0>

For canagliflozin vs. 2nd generation SUs

- Optum- <https://bwh-dope.aetion.com/projects/details/660/results/44834/result/0>
- Marketscan- <https://bwh-dope.aetion.com/projects/details/661/results/44835/result/0>
- Medicare- <https://bwh-dope.aetion.com/projects/details/662/results/44836/result/0>

Date conducted: 11/18/2019

After review of initial feasibility and power analyses, complete creation of the remaining covariates (see Table 1 below for list of covariates). Again, using the dummy outcome of a 90-day gap in database enrollment, complete a 1:1 PS-matched analysis. The PS should include the complete list of covariates (excluding laboratory values, which are missing in some patients).

- Provide plot of PS distributions stratified by treatment group.

Note- Please refer to **Appendix B**.

- Report covariate balance after matching.

Note- For Table 1, please refer to **Appendix B**.

- Report reasons for censoring by treatment group.

- For canagliflozin vs. DPP4i

	Overall	Referent	Exposure
Dummy Outcome	0 (0.00%)	0 (0.00%)	0 (0.00%)
Death	589 (0.39%)	374 (0.49%)	215 (0.28%)
Start of an additional exposure	6,913 (4.54%)	2,413 (3.17%)	4,500 (5.91%)
End of index exposure	98,215 (64.53%)	47,931 (62.98%)	50,284 (66.08%)
Specified date reached	22,353 (14.69%)	12,162 (15.98%)	10,191 (13.39%)
End of patient enrollment	19,170 (12.60%)	9,407 (12.36%)	9,763 (12.83%)
Switch to other DPP4i (for censoring) + nursing home admission	4,962 (3.26%)	3,814 (5.01%)	1,148 (1.51%)

- For canagliflozin vs. 2nd generation SUs

	Overall	Referent	Exposure
Dummy Outcome	0 (0.00%)	0 (0.00%)	0 (0.00%)
Death	548 (0.40%)	364 (0.53%)	184 (0.27%)
Start of an additional exposure	6,001 (4.36%)	1,842 (2.68%)	4,159 (6.04%)
End of index exposure	85,900 (62.38%)	41,024 (59.58%)	44,876 (65.18%)
Specified date reached	22,281 (16.18%)	12,957 (18.82%)	9,324 (13.54%)
End of patient enrollment	18,853 (13.69%)	9,660 (14.03%)	9,193 (13.35%)
Switch to other SUs (for censoring) + nursing home admission	4,117 (2.99%)	3,003 (4.36%)	1,114 (1.62%)

- Report follow-up time by treatment group.

- For canagliflozin vs. DPP4i

Median Follow-Up Time (Days) [IQR]			

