17	Investigator's assessment that the subject's life expectancy is less than 1 year, or any condition that in the opinion of the investigator would make participation not in the best interest of the subject, or could prevent, limit, or confound the protocol-specified safety or efficacy assessments.	Measured 180 days prior to drug initiation- CCI >=10	Gagne, Josh J et al. "A combined comorbidity score predicted mortality in elderly patients better than existing scores." J Clin Epidemiol . 2011 Jul;64(7):749-59. doi: 10.1016/j.jclinepi.2010.10.004. Sun, Jenny W et al. "Validation of the Combined Comorbidity Index of Charlson and Elixhauser to Predict 30-Day Mortality Across ICD-9 and ICD-10." Med Care . 2018 Sep;56(9):812. doi: 10.1097/MLR.0000000000000954.
18	Major surgery (i.e., requiring general anesthesia) within 3 months of the screening visit or any surgery planned during the subject's expected participation in the study (except minor surgery; i.e., outpatient surgery under local anesthesia).	Measured 90 days prior to drug initiation in any diagnosis position and inpatient or outpatient care setting- Major surgery selected from codes range 35.x-84.x	
19	Any condition that, in the opinion of the investigator, would compromise the well-being of the subject or prevent the subject from meeting or performing study requirements.	N/A	
20	Current use of other sodium glucose co-transporter 2 (SGLT2) inhibitor.	Measured 180 days prior to drug initiation as a dispensing of one of the following drugs- empagliflozin, dapagliflozin, ertugliflozin	
21	Known allergies, hypersensitivity, or intolerance to canagliflozin or its excipients.	N/A	

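### The primary as-treated rule does not censor comparator patients who add a non-canagliflozin SGLT2 inhibitor, although the plan bars the whole class at baseline

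*Combined protocol and SAP*

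**What the plan says.** Section 6.1 defines the exposure narrowly: "The study exposure of interest is initiation of canagliflozin". The same section makes the washout class-wide: "Initiation will be defined by no use of any SGLT-2 inhibitor or a comparator in the prior 6 months before treatment initiation". Appendix A, Exclusion 20, applies this to the other agents: "Measured 180 days prior to drug initiation as a dispensing of one of the following drugs- empagliflozin, dapagliflozin, ertugliflozin".

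Section 6.3.2 makes the as-treated analysis primary because it targets the hazard on treatment. Three of its rules matter here:

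- Follow-up is censored on augmentation or switching between canagliflozin and the comparator, in either direction, and on a move to another agent in the comparator class. The example given is one DPP4i replaced by another.
- For other drugs, "An added treatment that is not part of the exposure or comparator group does not fulfill this criterion". The example is a canagliflozin user who adds insulin.
- Stopping the index drug censors at the end of supply plus a 30-day grace period.

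The reasons-for-censoring table in Section 9 has a row labelled "Switch to other DPP4i (for censoring) + nursing home admission", with a matching row for other sulfonylureas in the second comparison. Neither table has a row for other SGLT2 inhibitors.

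**The concern.** The plan treats SGLT2 inhibitors as one class when it decides who may enter, and as separate drugs when it decides who stays in follow-up. Empagliflozin, dapagliflozin and ertugliflozin belong to neither the exposure group nor the comparator group. Read literally, the added-treatment rule therefore keeps a comparator patient who adds one of them in the referent arm.

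Section 5.1 uses DPP4 inhibitors as a stand-in for placebo. Time on a DPP4 inhibitor plus another drug of the exposure's own class fits that contrast poorly. If the other agents also lower MACE, the referent hazard falls, the HR moves toward 1, and power to reproduce 0.86 declines. The secondary sulfonylurea comparison uses the same rule. The ITT analysis drops switch and augmentation censoring by design, so the point concerns the as-treated analysis only.

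**Working it through.** **1. Do the written rules leave the gap?** Take a DPP4i user who starts empagliflozin.

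| What the patient does | Rule that applies | Result |
|---|---|---|
| Stops the DPP4i | Discontinuation | Censored at end of supply + 30 days |
| Continues the DPP4i and adds empagliflozin | Added treatment outside both groups | Not censored |

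The wording about switching in the reverse direction does not close the gap. It reverses a move from exposure to comparator, and the exposure is canagliflozin.

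**2. Is there a hidden category in the censoring tables?** Section 9, DPP4i comparison, referent arm: 374 + 2,413 + 47,931 + 12,162 + 9,407 + 3,814 = 76,101, the matched number. Sulfonylurea comparison, referent arm: 364 + 1,842 + 41,024 + 12,957 + 9,660 + 3,003 = 68,850, also the matched number. No separate category for other SGLT2 inhibitors has been left out. The row for starting an additional exposure is not defined. It most naturally means canagliflozin in the referent arm, but the platform setting cannot be checked from the documents.

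**3. The plan's own power (Section 10, pooled, DPP4i).**

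- Events D = 2 × 76,101 × 12.65/1,000 = 1,925.3553, as stated.
- Power = Φ(√(D/4) × |ln HR| − 1.96) = Φ(21.94 × 0.1508 − 1.96) = Φ(1.349) = 0.911. The stated figure is 0.911332398, so it is reproduced.

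**4. Size of a possible dilution.** Let f be the share of referent person-time on an added SGLT2 inhibitor and h that drug's hazard ratio for MACE. The documents give neither, so both are assumptions. With constant hazards the average referent hazard is multiplied by (1 − f + f·h), so

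expected HR = 0.86 / (1 − f + f·h).

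For f = 5% and h = 0.86: 0.86 / (0.95 + 0.043) = 0.86 / 0.993 = 0.866.

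Expected HR and power, holding D at 1,925.3553:

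| f | h = 1.00 | h = 0.86 | h = 0.75 |
|---|---|---|---|
| 1% | 0.860; 0.911 | 0.861; 0.906 | 0.862; 0.902 |
| 3.17% | 0.860; 0.911 | 0.864; 0.895 | 0.867; 0.880 |
| 5% | 0.860; 0.911 | 0.866; 0.884 | 0.871; 0.858 |

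The 3.17% row is illustrative only. That figure is the proportion of referent patients (2,413 of 76,101) in the undefined additional-exposure row. It is not a share of person-time, and not a count of other SGLT2 inhibitors.

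**The case against.** The strongest reply is that the effect is probably small and may be nil.

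- **Little such use is visible.** In the DPP4i flowcharts, Exclusion 20 removed 833 of 119,515, 892 of 130,586 and 817 of 306,414 patients: 2,542 of 556,515, or 0.46%. At f = 0.5% and h = 0.86 the HR would be 0.86/0.9993 = 0.8606 and power about 0.909. This count is before the index date and covers both arms, so it is indirect evidence on add-on use during follow-up. It does weigh against large shares.
- **Person-time is less than patients.** If 3.17% of patients added a drug halfway through follow-up, the share would be about 1.6% (3.17%/2). Median referent follow-up is short, 121 to 153 days. This stands.
- **Other antidiabetic drugs are allowed.** Section 5.1 says so. But that permission is general, whereas the plan singles out this class at entry, so it does not settle the matter.
- **The exposure is a single agent**, so there is no within-exposure switch to list. That explains the asymmetry in the wording; it does not deal with comparator patients who add a drug of the same class.
- **Censoring at intensification may be informative.** This stands as a cost. The plan already accepts the same kind of censoring when a comparator patient adds canagliflozin.

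A reader might infer that every comparator patient who starts another SGLT2 inhibitor is retained. The discontinuation rule contradicts that for patients who stop the comparator; 62.98% of referents end follow-up under that rule, for whatever reason.

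**Conclusion.** The gap is in the written rule: add-on use of a non-canagliflozin SGLT2 inhibitor, and overlap during the grace period, count as referent time in the primary analysis. This sits badly with the class-wide bar at baseline and with the on-treatment, placebo-proxy contrast.

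The consequence is conditional. If other SGLT2 inhibitors have a MACE effect of 0.86 and occupy 1% to 5% of referent person-time, the expected HR is 0.861 to 0.866 and power 0.906 to 0.884, against 0.86 and 0.911. If they have no effect on MACE, nothing changes. The calculation also assumes constant hazards and an unchanged number of events.

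Two stronger readings are not supported. One is that the HR is shown to be biased toward 1: the documents establish neither a MACE benefit of the other agents nor how much time is affected. The other is a large loss of power. A 10% share with h = 0.86 would give 0.872 and 0.851, but nothing in the documents points to a share of that size. The point merits a correction because it is cheap and concerns the primary estimand, even though the likely shift is modest.

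**What to change.** Amend the switching and augmentation bullet in Section 6.3.2 so that, in both arms, as-treated follow-up is also censored at the first dispensing of any SGLT2 inhibitor other than the index drug, using the class list in Appendix A. State that the added-treatment exception does not cover this class. Define the additional-exposure row in Section 9, and report starts of other SGLT2 inhibitors by arm as a row of their own. Show the result without this censoring as a sensitivity analysis.

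The cost is one line of text, an existing drug list and one extra run. The counts can come from the dummy-outcome run of Section 9, without looking at study outcomes, and the date field for the comparative analyses in Section 13 is still blank. The downside is slightly more, possibly informative, censoring, which the sensitivity analysis is there to show.

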5.2 Important steps for cohort formation

5.2.1 Eligible cohort entry dates

Market availability of canagliflozin in the U.S. started on March 29, 2013.

- For Marketscan and Medicare: April 1, 2013-Dec 31, 2017 (end of data availability).
- For Optum: April 1, 2013-March 31, 2019 (end of data availability).

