Appendix A

#	CANVAS trial definitions	Implementation in routine care	References/Rationale	Color coding
	Trial details- Secondary indication, 4a- unintended superiority with label change		Please see the following Google Drive for further details or any missing information: https://drive.google.com/open?id=1WD618wrvwYIeaXzfLTcuKVcnnb6b-eV	Criteria
	EXPOSURE vs. COMPARISON		ICD-10 codes are not listed in this document because of excel cell size limitations and excessive number of ICD-10 codes. Full ICD-10 code lists will be available in the above Google Drive Folder (link above). ICD-9 to ICD-10 code conversions were completed using a SAS macro that implements forward/backward mapping based on the CMS ICD-9 to ICD-10 mapping: https://www.nbr.org/data/icd9-icd-10-cm-and-pcs-crosswalk-general-equivalence-mapping.html	Adequate mapping in claims
	Canagliflozin vs. placebo	Canagliflozin vs. DPP4 inhibitors (primary comparison) or vs. 2nd generation sulfonylureas (secondary)	Patorno, [name] et al. "Cardiovascular outcomes associated with canagliflozin versus other non-glipizid antidiabetic drugs: population based cohort study." BMJ 2018;360:k119 http://dx.doi.org/10.1136/bmj.k119	Intermediate mapping in claims
	PRIMARY OUTCOME			Poor mapping or cannot be measured in claims

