1	Man or woman with a diagnosis of type 2 diabetes with glycated hemoglobin level $\geq 7.0\%$ to $\leq 10.5\%$ at screening and be either:	Patients with a diagnosis of T2DM (ICD-9 Dx code of 250.x0 or 250.x2) in the 180 days prior to drug initiation in any diagnosis position and inpatient or outpatient care setting.	Patorno, [name] et al. "Cardiovascular outcomes associated with canagliflozin versus other non-glipizid antidiabetic drugs: population based cohort study." BMJ 2018;360:k119 http://dx.doi.org/10.1136/bmj.k119	
	o (1) not currently on antihyperglycemic agent (AHA) therapy or o (2) on AHAmonotherapy or combination therapy with any approved class of agents: e.g., sulfonylurea, metformin, peroxisome proliferator-activated receptor gamma (PPAR γ) agonist, alpha-glucosidase inhibitor, glucagon-like peptide-1 (GLP-1) analogue, dipeptidyl peptidase-4 (DPP-4) inhibitor, or insulin.	Depending on the comparison group, we will require new-use (defined as no use 180 days prior to index date) of canagliflozin and a comparator drug	Patorno, [name] et al. "Empagliflozin and the Risk of Heart Failure Hospitalization in Routine Clinical Care: A First Analysis from the Empagliflozin Comparative Effectiveness and Safety (EMPRISE) Study." Circulation . 2019 Apr 8. doi: 10.1161/CIRCULATIONAHA.118.039177	
2	History or high risk of cardiovascular disease defined on the basis of either:			
	- Age ≥ 30 years with documented symptomatic atherosclerotic cardiovascular disease:	Age ≥ 30 years at drug initiation		
	o including stroke;	Measured 180 days prior to drug initiation in any diagnosis position and inpatient or outpatient care setting- Any stroke: ICD-9 Dx: 430.xx, 431.xx, 433.xx, 434.xx, 436.xx	Patorno, [name] et al. "Cardiovascular outcomes associated with canagliflozin versus other non-glipizid antidiabetic drugs: population based cohort study." BMJ 2018;360:k119 http://dx.doi.org/10.1136/bmj.k119	
	o or myocardial infarction (MI);	Measured 180 days prior to drug initiation in any diagnosis position and inpatient or outpatient care setting- Acute MI ICD-9 410.xx, Old MI: 412.xx	Patorno, [name] et al. "Empagliflozin and the Risk of Heart Failure Hospitalization in Routine Clinical Care: A First Analysis from the Empagliflozin Comparative Effectiveness and Safety (EMPRISE) Study." Circulation . 2019 Apr 8. doi: 10.1161/CIRCULATIONAHA.118.039177	

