...median [IQR]	1.00 [0.00, 1.00]	1.00 [0.00, 2.00]	1.00 [0.00, 1.00]	1.00 [0.00, 2.00]	1.00 [0.00, 1.00]	1.00 [1.00, 2.00]	1.00 [0.94]	1.00 (1.00)	0.00
Number of creatinine tests ordered									
...mean (sd)	0.04 (0.28)	0.03 (0.22)	0.04 (0.26)	0.04 (0.24)	0.07 (0.32)	0.07 (0.33)	0.06 (0.30)	0.05 (0.28)	0.03
...median [IQR]	0.00 [0.00, 0.00]	0.00 [0.00, 0.00]	0.00 [0.00, 0.00]	0.00 [0.00, 0.00]	0.00 [0.00, 0.00]	0.00 [0.00, 0.00]	0.00 [0.30]	0.00 [0.28]	0.00
Number of BUN tests ordered									
...mean (sd)	0.03 (0.22)	0.02 (0.17)	0.03 (0.21)	0.02 (0.18)	0.04 (0.26)	0.04 (0.26)	0.04 (0.24)	0.03 (0.22)	0.04
...median [IQR]	0.00 [0.00, 0.00]	0.00 [0.00, 0.00]	0.00 [0.00, 0.00]	0.00 [0.00, 0.00]	0.00 [0.00, 0.00]	0.00 [0.00, 0.00]	0.00 [0.24]	0.00 [0.22]	0.00
Number of tests for microalbuminuria									
...mean (sd)	0.85 (1.20)	0.84 (1.16)	0.64 (1.04)	0.76 (1.11)	0.50 (0.72)	0.53 (0.72)	0.60 (0.91)	0.68 (0.98)	-0.08
...median [IQR]	0.00 [0.00, 2.00]	0.00 [0.00, 2.00]	0.00 [0.00, 1.00]	0.00 [0.00, 2.00]	0.00 [0.00, 1.00]	0.00 [0.00, 1.00]	0.00 [0.91]	0.00 [0.98]	0.00
Total N distinct ICD9/ICD10 diagnoses at the 3rd digit level									
...mean (sd)	6.16 (6.85)	5.46 (5.86)	2.67 (4.07)	2.01 (3.26)	5.84 (7.61)	5.73 (6.80)	5.21 (6.82)	4.46 (5.63)	0.12
...median [IQR]	5.00 [0.00, 9.00]	5.00 [0.00, 8.00]	0.00 [0.00, 4.00]	0.00 [0.00, 4.00]	4.00 [0.00, 9.00]	4.00 [0.00, 9.00]	3.33 (6.82)	2.96 (5.63)	0.06
Use of thiazide; n (%)	13,054 (14.0%)	2,752 (12.9%)	12,759 (12.9%)	3,416 (12.7%)	39,231 (15.2%)	5,305 (15.1%)	65,044 (14.4%)	11,473 (13.8%)	0.02
Use of beta blockers; n (%)	39,244 (42.2%)	7,904 (37.0%)	37,716 (38.1%)	9,582 (35.6%)	131,430 (50.8%)	17,160 (48.9%)	208,390 (46.2%)	34,646 (41.6%)	0.09
Use of calcium channel blockers; n (%)	32,362 (34.8%)	6,181 (29.0%)	31,378 (31.7%)	7,884 (29.3%)	97,784 (37.8%)	11,964 (34.1%)	161,524 (35.8%)	26,029 (31.2%)	0.10

Table 1

PS-matched										
	Optum		MarketScan		Medicare		POOLED			
Variable	Reference-DPP4i 19532	Exposure-Canagliflozin 19532	Reference-DPP4i 23168	Exposure-Canagliflozin 23168	Reference-DPP4i 33401	Exposure-Canagliflozin 33401	Reference-DPP4i 76,101	Exposure-Canagliflozin 76,101	St. Diff.	
Number of patients										
Age										
...mean (sd)	62.47 (8.28)	62.59 (7.93)	59.39 (7.08)	59.50 (6.58)	71.02 (5.32)	71.06 (5.19)	65.28 (6.73)	65.37 (6.41)	-0.01	

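### The propensity score omits calendar year or quarter of cohort entry, and its balance is not reported, over a 4.75 to 6 year entry window that opens at canagliflozin's launch

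*Combined protocol and SAP*

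**What the plan says.** Section 6.2 starts from age, sex and the comorbidity index and defers the rest to Appendix B: "Remaining covariates are defined only after the study has passed the initial feasibility analysis and the initial power assessment and are listed in Table 1". Section 9 then sets the final PS: "The PS should include the complete list of covariates (excluding laboratory values, which are missing in some patients". Matching is 1:1 on that score. Neither Section 9 nor Section 13 mentions matching, stratifying or adjusting on entry date. The trimmed secondary analysis in Section 13.2 reuses deciles of the same score.

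Section 5.2.1 gives the calendar frame. On launch: "Market availability of canagliflozin in the U.S. started on March 29, 2013". On the entry windows: "For Marketscan and Medicare: April 1, 2013-Dec 31, 2017 (end of data availability" and "For Optum: April 1, 2013-March 31, 2019 (end of data availability". Appendix A adds that two coding systems fall within the study: "ICD-9 to ICD-10 code conversions were completed using a SAS macro that implements forward/backward mapping".

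Section 10 stops the work until the investigators, FDA and advisory board members have reviewed covariate balance. Table 1 is what they review it from.

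**The concern.** Canagliflozin was new at the start of the window, while the comparator classes are long-standing. Initiators of a new drug may be spread over the following years differently from initiators of its comparators. A common window bounds entry dates in both arms but does not give them the same distribution.

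The setting also changed inside the window. Outcomes are defined by ICD-9 codes plus mapped ICD-10 codes, and the drug list in Appendix A dates several antidiabetic approvals and one withdrawal between 2014 and 2017. If event rates or outcome capture drifted over the window, and the arms entered at different times, the matched HR would carry part of that drift. The target HR is 0.86, so a shift of a few percent bears on how closely the trial result appears to be reproduced. The Section 10 reviewers have no row with which to rule this out.

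**Working it through.** **1. Is entry period in the list?** I read the rows of Table 1, unmatched and matched, for both comparators. They cover age, gender, race (Medicare only), region, cardiovascular history, diabetes complications, other comorbidities, diabetes and other drugs, laboratory values, comorbidity and frailty scores, and healthcare use. None gives year, quarter or date of entry.

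**2. Window against follow-up.** 1 April 2013 to 31 December 2017 is 1,736 days (1,736/365.25 = 4.75 years). To 31 March 2019 it is 2,191 days (6.00 years). The shorter window applies to (23,168 + 33,401)/76,101 = 74% of matched patients in each arm of the DPP4i comparison. Median follow-up comes from the overall rows in Section 9, because the arm-specific rows print identical figures for MarketScan and Medicare.

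| Comparison | Optum | MarketScan | Medicare |
|---|---|---|---|
| DPP4i | 127/2,191 = 5.8% | 149/1,736 = 8.6% | 147/1,736 = 8.5% |
| Sulfonylurea | 141/2,191 = 6.4% | 159/1,736 = 9.2% | 172/1,736 = 9.9% |

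A typical patient is therefore observed for 6 to 10% of the window.

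**3. The plan's own precision, reproduced.** Section 10 expects 1,925.36 pooled events against DPP4i. The SE of the log HR is 2/√1,925.36 = 0.0456. Superiority power at HR 0.86 is Φ(|ln 0.86|/0.0456 − 1.96) = 0.911, as stated. Non-inferiority power at margin 1.3 is 0.9999, also as stated.

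**4. Illustration; both inputs are assumed.** Split the window in half. Let RR be the hazard ratio between halves, and p1 and p0 the proportions of each arm entering in the later half, centred at 0.5. The bias factor on the HR is (1 + p1(RR − 1))/(1 + p0(RR − 1)). RR is taken as 0.8 and 1.2, with both signs of imbalance.

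| Arm difference in entry half | Standardized difference | Bias factor | Largest shift in SE | A true 0.86 would read |
|---|---|---|---|---|
| 5 points | 0.10 | 0.989 to 1.011 | 0.24 | 0.850 to 0.870 |
| 10 points | 0.20 | 0.978 to 1.022 | 0.49 | 0.841 to 0.879 |

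For example, at 10 points and RR 0.8: (1 − 0.2 × 0.55)/(1 − 0.2 × 0.45) = 0.89/0.91 = 0.978, and |ln 0.978|/0.0456 = 0.49. If the three database risks are weighted by matched counts, expected events become 2,165 and the largest shifts are 0.26 and 0.52 SE.

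**5. Which conclusion is exposed.** With a true HR of 1 and a factor of 1.022, non-inferiority power is Φ(ln(1.3/1.022)/0.0456 − 1.96) = 0.9995. The non-inferiority reading is hardly touched. What is exposed is the point estimate and the superiority comparison with 0.86.

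**The case against.** The strongest reply is that nothing in the documents shows an imbalance or a trend, and that existing covariates may already absorb part of the problem. Both parts have force.

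The most relevant covariate is the row "Total N distinct ICD9/ICD10 diagnoses at the 3rd digit level". Its lower quartile is 0 in every database, yet inclusion criterion 1 requires "Patients with a diagnosis of T2DM (ICD-9 Dx code of 250.x0 or 250.x2) in the 180 days prior to drug initiation", so the row cannot be counting all codes. If it counts one code system, which is an inference, it would track coding era. In the DPP4i comparison its pooled standardized difference falls from 0.12 to 0.01 after matching. Matched means are 5.59 vs 5.54 (Optum), 2.18 vs 2.12 (MarketScan) and 5.83 vs 5.75 (Medicare), with identical medians and quartiles by arm. On that reading a large difference in coding era is unlikely. The row would still say little about entry year within an era, and if the inference is wrong it says nothing about either.

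The assumed RR range is also wide. Across half-window midpoints about 2.4 years apart, 0.8 corresponds to a fall of roughly 9% a year and 1.2 to a rise of about 8%. A flatter trend gives smaller factors.

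A reader might infer from Section 9's censoring table that referents did enter later. Censoring at the administrative end date is 15.98% vs 13.39% against DPP4i and 18.82% vs 13.54% against sulfonylureas, higher in the referent arm both times. The documents do not support that step, because longer time on drug raises the same count. For sulfonylureas the ratio 18.82/13.54 = 1.39 equals the ratio of median follow-up printed for MarketScan and Medicare, 200/144 = 1.39.

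**Conclusion.** The omission is established from Sections 6.2, 9 and 13 and Table 1. Entry period is neither adjusted for directly nor shown to the people asked to approve balance. I could not see the design diagram or the PS plots, but the plan defines its covariates by Table 1.

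How much it matters is not established. A reader might conclude that the matched HR is biased, or that superiority power is materially overstated. Neither follows: the documents give no entry-date distribution by arm and no secular trend, so neither the size nor the sign of any effect can be derived. The factors of 0.989 to 1.011 and 0.978 to 1.022 are illustrations on assumed inputs and run in both directions. Larger arm differences would give larger factors, but nothing in the documents supports them and the balanced diagnosis-count row argues mildly against them. This is an inexpensive safeguard that the plan should have, not a demonstrated error in its result.

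**What to change.** Before Section 13 is run:

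1. Tabulate year or quarter of cohort entry by arm, within each database, in the existing matched cohorts for both comparators. This needs no re-match and shows how much a re-match is likely to change.
2. Add entry year or quarter to the PS within each database, or match within it, and re-run the match.
3. Add entry period to Table 1 for both comparators, before and after matching, and update the balance, censoring and power outputs of Sections 9 and 10.

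The cohort entry date already exists for every patient. The date field for Section 13 is blank and the matching used a dummy outcome, so on the document's own record the change can precede any comparative result. The cost is repeating outputs that were reviewed on 12/9/19 and 12/20/19, and possibly losing a few matched pairs. The matched number and power after the change cannot be computed from the documents.
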